9.2.4. Grading of Specific Adverse Events in the Pregnant Women and their Infants

Table 8: Maternal and Infant Adverse Events

Maternal Adverse Events (Adverse Events during Pregnancy)				
Parameter	Normal	Grade 1	Grade 2	Grade 3
Pregnancy loss (Pregnancy does not result in a live birth)	None	N/A	N/A	Spontaneous abortion or miscarriage
Spontaneous abortion or miscarriage in the first or second trimester of gestation				
Fetal death at or after 20 weeks of gestation (stillbirth)				
Bleeding (vaginal) during pregnancy prior to the onset of labor	None	Spotting or bleeding less than menses	Bleeding like menses or heavier, no intervention indicated	Profuse bleeding with dizziness or orthostatic hypotension, transfusion indicated
Postpartum hemorrhage	EBL ^c ≤500 cc for vaginal delivery or ≤1000 cc after CS or reported as normal	EBL 501-1000 for vaginal delivery or 1001-1500 for CS or reported as slightly increased	EBL >1000 for vaginal delivery or >1500 for CS, with or without mild dizziness, no transfusion required	Hemorrhage at a level for which transfusion of packed cells or any amount of other blood components is indicated
Postabortal endometritis/salpingitis	None	Low grade fever and uterine tenderness, resolved with oral antibiotics	Moderate symptoms, requiring ≤3 days of parenteral antibiotics	Severe symptoms requiring >3 days of IV antibiotics or development of TOA
Preterm rupture of membranes	None	N/A	Preterm rupture but not resulting in delivery before 37 weeks gestation	Preterm rupture resulting in delivery before 37 weeks gestation

Preterm contractions /labor/delivery^e	None Braxton Hicks contractions (as early as second trimester)	Preterm contractions which resolve without medical intervention	Preterm contractions with cervical change which result in medical intervention but not resulting in preterm delivery	Delivery before 37 weeks gestation
Poor fetal growth If infant is small for gestational age on newborn exam: report as NEONATAL OUTCOME based on birth weight (see below)	At or above 10 th percentile	Fetal growth <10 th percentile but ≥3 rd percentile for gestational age by ultrasound	N/A	Fetal growth <3 rd percentile for gestational age by ultrasound
Hypertension, preeclampsia/eclampsia	None	Pregnancy induced hypertension	Preeclampsia	HELLP syndrome, or eclampsia,

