Chorioamnionitis	None	Fever (38°C–38.4°C or 100.4°F–100.9°F) with two or more: FHR ^e >160 BPM ^f , maternal HR >120, uterine tenderness between contractions or purulent AF or preterm labor	Same as Grade 1 plus fever 38.5°C–40°C or 101°F–104°F	Criteria for Grade 2 plus fetal distress or fever >40°C or 104°F
Postpartum endometritis	None	Low grade fever and uterine tenderness, resolved with oral antibiotics	Moderate symptoms, treated by ≤3 days of parenteral antibiotics	Severe symptoms treated with >3 days of IV antibiotics, addition of heparin, or operative intervention
Gestational diabetes mellitus	N/A	New onset controlled by diet	New onset with initiation of medical therapy	Uncontrolled despite treatment modification
Clinical AE, pregnancy-related, NOT identified elsewhere in this AE Grading Table	None	Symptoms causing no or minimal interference with usual social & functional activities	Symptoms causing greater than minimal interference with usual social & functional activities	Symptoms causing inability to perform usual social & functional activities

Mode of delivery^f (normal spontaneous vaginal delivery, induced delivery, assisted vaginal delivery, Caesarean Section)	Not reported as AE/SAE. Mode of delivery is a procedure and should not be reported or graded as an AE/SAE. The reason for selecting the mode of delivery (for example: Caesarean Section for severe preeclampsia) should be reported and graded as appropriate.
--	---

**Infant Adverse Events
(Neonatal and Infant Events)**

Parameter	Normal	Grade 1	Grade 2	Grade 3
Preterm birth^g	Born after 36 6/7 weeks gestation	Late preterm: 34 to 36 6/7 weeks gestation	Early preterm: 32 to 33 6/7 weeks gestation	Very or extremely preterm: ≤ 31 6/7 weeks gestation
Birth weight (grams)^g (Small, appropriate, large for gestational age)	Birth weight ≥2500		Low birth weight: 1501-2500	Very low birth weight ≤1500
Report separately poor fetal growth (as above)				
Neonatal complications in a term infant	Normal term infant discharged home with mother after uncomplicated delivery and nursery course	Transient signs and symptoms requiring no interventionⁱ , and resolved spontaneously ^h	Signs/symptoms requiring interventionⁱ but discharged home with mother (± 2 days) , or close to it	Required NICU for more than 1 week, and/or interventions (including surgery) leading to prolonged hospitalization (report SAE) ^j

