9.5. Halting Rules

For pregnant women, further enrollment and study vaccinations will be halted for DSMB review/recommendation if any of the following are reported:

- Any subject experiences ulceration, abscess, or necrosis at the injection site related to study product administration.
- Any subject experiences laryngospasm, bronchospasm, or anaphylaxis within 1 day after administration of study product that is considered related to study product.

- Two or more subjects experience generalized urticaria within 3 days after administration of study product that is considered related to study product.
- Any subject experiences a study vaccine-related SAE from the time of study vaccination through subject's last study visit.
- Any subject experiences acute weakness of limbs and/or cranial nerve innervated muscles (description of potential signal of GBS) after administration of study vaccine.

For pregnant women, this study will also be halted for DSMB review/recommendation if, within 7 days after administration of the study vaccination, any of the following occurs:

- 5% or more of subjects (with a minimum of 5 subjects) who received study vaccine experience the same severe (Grade 3) study vaccine-related injection site reaction.
- 5% or more of subjects (with a minimum of 5 subjects) who received study vaccine experience the same severe (Grade 3) study vaccine-related subjective systemic reaction with the exception of allergic reaction, for which the severity (grade) is corroborated by study personnel.
- 5% or more of subjects (with a minimum of 5 subjects) who received study vaccine experience the same severe (Grade 3) study vaccine-related quantitative systemic reaction.
- 5% or more of subjects (with a minimum of 5 subjects) who received study vaccine experience the same severe (Grade 3) pregnancy-related AEs, as found in [Section 9.2.4](#), that are deemed study-vaccine related.

Grading scales for solicited local (injection site) and systemic (subjective and quantitative) reactions are included in [Section 9.2.2](#). Solicited injection site measurements will not be used to halt the study.

If any of the halting rules are met following any subject receipt of study vaccination, then this study will not continue with the remaining enrollments or study vaccinations without a review by and recommendation from the DSMB to proceed.

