DMID retains the authority to suspend additional enrollment and study interventions/administration of study product during the entire study, as applicable.

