9.6. Safety Oversight (ISM plus SMC or DSMB)

9.6.1. Independent Safety Monitor (ISM)

The ISM is a physician with relevant expertise whose primary responsibility is to provide independent safety monitoring in a timely fashion. Participation is for the duration of the trial and is a voluntary position that does not receive payment. The ISM must meet the requirements of the NIAID conflict of interest policy.

The ISM:

- Will have experience in obstetrics.
- Is in close proximity to the study site and has the authority and ability to readily access subject records in real time.
- May be a member of the participating institution's staff but preferably be from a different organizational group within the institution.
- Should not be in a direct supervisory relationship with the investigator.
- Should have no direct involvement in the conduct of the study.

The ISM will:

- Sign a Conflict of Interest (COI) certification at the time they are asked to participate and provide updates to this information as needed.
- Receive reports of Serious Adverse Events (SAEs) deemed related to the study from the site investigator and will be notified by email when DMID is notified of the SAE.
- Receive reports from the site investigator of any subject who experiences acute weakness of limbs and/or cranial nerve innervated muscles (description of potential signal of GBS) after administration of study vaccine.
- Evaluate the SAE and report their clinical assessment to DMID, through DMID-CROMS SOCS in a timely manner using the attached report form and email the report to DMID-CROMS SOCS.
- Communicate with the investigator at the participating site as needed.
- Review additional safety related events at the request of DMID.
- Provide additional information to DMID and/or the DSMB by teleconference as requested.

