9.6.2. Data and Safety Monitoring Board (DSMB)

Safety oversight will be conducted by a DSMB that is an independent group of experts that monitors subject safety and advises DMID. The DSMB members will be separate and independent of study personnel participating in this trial and should not have scientific, financial, or other conflicts of interest related to this trial. The DSMB will consist of members with appropriate expertise to contribute to the interpretation of the data from this trial.

The DSMB will operate under the rules of a DMID-approved charter that will be written at the organizational meeting of the DSMB. Procedures for DSMB reviews/meetings will be defined in the charter. Reports may include enrollment and demographic information, medical history, concomitant medications, physical assessments, clinical laboratory values, dosing compliance,

and solicited and unsolicited AE/SAEs. The DSMB will review SAEs on a regular basis and ad hoc during this trial. The DMID Medical Monitor and the ISM (as deemed necessary per [Section 9.6.1](#)) will be responsible for reviewing SAEs in real time.

Additional data may be requested by the DSMB, and interim statistical reports may be generated as deemed necessary and appropriate by DMID. The DSMB may receive data in aggregate and presented by treatment arm (pregnant women, infants). The DSMB may also be provided with expected and observed rates of the solicited AEs in an unblinded fashion and may request the treatment assignment be unblinded for an individual subject if required for safety assessment.

The DSMB will review grouped and unblinded data in the closed session only. As an outcome of each review/meeting, the DSMB will make a recommendation as to the advisability of proceeding with study vaccinations (as applicable), and to continue, modify, or terminate this trial.

The DSMB will conduct the following reviews:

- When safety data collected through Day 8 is available for 25% of pregnant study subjects.
- Ad hoc when a halting rule is met or DMID/DSMB chair may convene an ad hoc meeting if there are immediate concerns regarding observations during this trial.
- Final review meeting: 6 to 8 months after clinical database lock to review the cumulative unblinded data for this trial. The data will be provided in a standard summary format. The DSMB may be asked to provide recommendations in response to questions posed by DMID.

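### Protocol 9.4, the V05–V08 visit text and the Appendix A footnote stop recording non-serious maternal events at Day 31 or delivery, although pregnancy-specific events are a primary outcome that SAP 9.5 collects throughout; the 7-day halting window is a secondary matter for the DSMB

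*Protocol*

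**What the plan says.** **The endpoint.** Protocol 3.2.1 makes the frequency and severity of the pregnancy-specific events in 9.2.4 a primary safety outcome and gives no end date. Section 9.1 lists them as item 2, apart from unsolicited non-serious events (item 4); of those two items, only item 4 has a Day 31 limit. Table 8 in 9.2.4 grades events that occur late or after birth, including postpartum hemorrhage and postpartum endometritis. Its footnote e asks for a maternal and an infant AE for each preterm delivery. SAP 9.5 says pregnancy-related events are collected and graded for the whole study.

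**The recording instructions.**
- Protocol 9.4 ends collection of non-serious AEs in pregnant women at the earlier of Day 31 and delivery.
- The Appendix A footnote to the maternal AE row, repeated in SAP Table 2, allows only serious events and new chronic conditions after that point.
- The delivery visit text (V05) takes AEs only within 30 days of vaccination.
- V06, V07 and V08 ask staff to record new congenital anomalies and SAEs.
- Section 9.3 applies the same limit to unsolicited non-serious AEs and does not say whether Table 8 events belong to that class.

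**The halting rule.** Protocol 9.5 has one numeric criterion specific to pregnancy: at least 5% of vaccinated women, and at least 5, who "experience the same severe (Grade 3) pregnancy-related AEs" judged related to vaccine. It stands in the list introduced by "this study will also be halted for DSMB review/recommendation if, within 7 days after administration of the study vaccination, any of the following occurs". A separate rule halts the study if "Any subject experiences a study vaccine-related SAE from the time of study vaccination through subject's last study visit".

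**The concern.** The two sets of instructions cannot both be followed. If sites work from 9.4 and the schedule, a primary safety outcome is cut off before much of it can occur. Events that were never recorded cannot be recovered at analysis, and the tables would show them as absent. Because assessors are blinded, the shortfall should fall on both arms alike. The expected harm is therefore understated frequencies and a weaker comparison, with no reason to expect a spurious difference between arms.

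The halting window raises a related question. Vaccination is at 14 0/7 to 26 6/7 weeks, so each woman's 7-day count closes by 27 6/7 weeks. Table 8 treats "delivery before 37 weeks gestation", fetal growth below the 3rd percentile and gestational diabetes that is "Uncontrolled despite treatment modification" as Grade 3, and these mostly arise later.

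**Working it through.** The plan states no figure for either window, so there is nothing to reproduce.

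**1. Does the Day 31 limit reach Table 8 events?** The documents do not settle this.
- Protocol 9.1 keeps the two classes apart, and SAP Table 45 has one row for unsolicited non-serious events through Day 31 and another, undated, for pregnancy-related events.
- SAP 9.3.2, however, lists the pregnancy-related summaries (Tables 77 and 78) among the unsolicited AE outputs, while the title of SAP Table 8 puts the same events on the solicited grading scale.
- Protocol 9.4 and the Appendix A footnote make no exception for Table 8 events.

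**2. Where Day 31 falls.** Day 31 is vaccination plus 30 days.
- Vaccinated at 14 0/7: Day 31 is 18 2/7 weeks. Time to 37 0/7 is 161 days, and the share after Day 31 is (161 − 30)/161 = 81%.
- Vaccinated at 26 6/7: Day 31 is 31 1/7 weeks. Time to 37 0/7 is 71 days, and the share after Day 31 is (71 − 30)/71 = 58%.

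Under 9.4 the window closes at delivery at the latest, so a non-serious postpartum event can never fall inside it. That conclusion needs no assumed rate.

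**3. What would be missed after the window closes, if the event is not serious.**

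| Maternal event in Table 8 | Other route into the data |
|---|---|
| Postpartum hemorrhage, Grade 1–2 | None as a graded AE |
| Postpartum endometritis, non-serious | None as a graded AE |
| Late gestational diabetes | Only if classed as a new chronic condition, or inferred from medications recorded to delivery discharge |
| Pregnancy-induced hypertension | Only if pressure is raised at V05 (graded under Table 7, shown in SAP Table 68) |
| Preterm delivery | Captured: Table 8 footnote e and birth outcomes |

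**4. How the SAP treats an unrecorded event.** SAP 9.3 uses the full population as denominator for incidence, and SAP 6.5 plans no imputation. An unrecorded hemorrhage would therefore enter Table 81 as none and count as a non-event in Table 77 and in the Fisher's exact comparison in Table 79.

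**5. Halting window.** Seven days is 7/161 = 4.3% to 7/71 = 9.9% of the time to 37 weeks. The documents give no event rates, so what follows is illustrative. The simulation (20,000 trials per setting) assumes 200 women accrued evenly over 26 weeks, even gestational age at vaccination and one event type. A trigger needs at least 5 events and 5% of women vaccinated so far, no later than the last vaccination. The range in each row below is for deliveries at 34–37 and at 28–37 weeks.

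| Delivery before 37 weeks, 10% rate | 7-day count | Count to last visit |
|---|---|---|
| 25% judged related | 0% | 0.005–0.13% |
| 50% judged related | 0% | 1.2–6.0% |
| 100% judged related | 0% | 34.6–65.8% |

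This leaves out the rule that one related SAE halts the study. With 50–100% judged related, on average 23–47 women are still unvaccinated at the trigger. That means 153–177 are vaccinated, and the threshold is 8–9 events (0.05 × 153 = 7.65; 0.05 × 177 = 8.85). If 25% of related preterm deliveries were serious (an assumption), the chance that none of 8 is serious is 0.75^8 = 0.10; at 50% it is 0.5^8 = 0.004. At 50% relatedness and 25% seriousness, the added triggers shrink to roughly 0.10 × (1.2–6.0%) = 0.1–0.6%.

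**The case against.** The best defence is that pregnancy events are a category of their own and that the Day 31 wording was written for ordinary AEs. Protocol 9.1, footnote e, SAP Table 45 and the dedicated outputs (SAP Tables 77–82, Listing 13) support this. Much also survives outside AE recording: birth outcomes, blood pressure at delivery, interim histories, chart review, and infant AEs to day 180 if medically attended. This stands as evidence of intent, and it rules out a reading that some may infer, namely that the primary outcome will certainly be lost or that preterm delivery goes unrecorded. It does not remove the contradiction. Section 9.4 and Appendix A are what a site follows visit by visit, and none of the other routes yields a graded maternal AE with a relatedness judgment.

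On halting, a reader might infer that late pregnancy harm is unmonitored. It is not. Any one related SAE halts the study through the last visit, and the DSMB reviews SAEs regularly. There are also discretionary powers: "DMID retains the authority to suspend additional enrollment and study interventions/administration of study product during the entire study, as applicable"; the "DMID/DSMB chair may convene an ad hoc meeting if there are immediate concerns"; and the independent safety monitor may "Review additional safety related events at the request of DMID". Nor do the documents support a large gain from a longer window. The 35–66% range needs every event judged related, and all the simulated gains leave seriousness out. The exclusion of women at high obstetric risk may also lower event rates. A longer window has its own cost: for events spread evenly from vaccination to 37 weeks at a 10% rate with half judged related, one event type alone would pause 21.5% of trials, before allowing for seriousness, and Table 8 has about a dozen maternal types.

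**Conclusion.** The recording conflict is real and worth correcting. As written, Protocol 9.4, V05–V08 and Appendix A exclude every non-serious postpartum event, and any non-serious antenatal event in the 58–81% of the vaccination-to-37-week period after Day 31, from a primary outcome that SAP 9.5 says is collected throughout. The window arithmetic rests on no assumed rates. How much data would be lost is unknown: it depends on which instruction sites follow, and the case report form instructions that might settle this are not in the documents. This is a risk of falsely empty rows, not proof of missing data.

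The halting window is secondary. Section 9.5 has no count for related, non-serious Grade 3 pregnancy events after Day 8, but the practical gain from adding one is small. It depends on assumed rates, seriousness and relatedness, and it protects only women not yet vaccinated: under the same accrual assumptions, about 72 of 200 women pass 37 weeks before the last vaccination.

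**What to change.** **Recording.** State the same rule in Protocol 9.3, 9.4, the V05–V08 visit text, the Appendix A footnote and the SAP Table 2 footnote: maternal events in Table 8, including non-serious ones, are recorded with grade and relatedness from vaccination through the last study visit. Leave the Day 31 limit in place for other non-serious events. The cost is an amendment limited to wording and some extra AE recording at delivery and postpartum visits that already take place.

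**Halting, for DSMB agreement.** Consider moving the pregnancy-related criterion in 9.5 out of the 7-day list and counting through the last study visit while vaccinations continue. Keep the 5% and minimum-5 threshold and the relatedness condition. The cost is one moved bullet and an added chance of a pause, which the DSMB should weigh across all Table 8 event types. The longer count works only if the recording change is also made.

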9.6. Safety Oversight (ISM plus SMC or DSMB)

9.6.1. Independent Safety Monitor (ISM)

The ISM is a physician with relevant expertise whose primary responsibility is to provide independent safety monitoring in a timely fashion. Participation is for the duration of the trial and is a voluntary position that does not receive payment. The ISM must meet the requirements of the NIAID conflict of interest policy.

The ISM:

- Will have experience in obstetrics.
- Is in close proximity to the study site and has the authority and ability to readily access subject records in real time.
- May be a member of the participating institution's staff but preferably be from a different organizational group within the institution.
- Should not be in a direct supervisory relationship with the investigator.
- Should have no direct involvement in the conduct of the study.

The ISM will:

- Sign a Conflict of Interest (COI) certification at the time they are asked to participate and provide updates to this information as needed.
- Receive reports of Serious Adverse Events (SAEs) deemed related to the study from the site investigator and will be notified by email when DMID is notified of the SAE.
- Receive reports from the site investigator of any subject who experiences acute weakness of limbs and/or cranial nerve innervated muscles (description of potential signal of GBS) after administration of study vaccine.
- Evaluate the SAE and report their clinical assessment to DMID, through DMID-CROMS SOCS in a timely manner using the attached report form and email the report to DMID-CROMS SOCS.
- Communicate with the investigator at the participating site as needed.
- Review additional safety related events at the request of DMID.
- Provide additional information to DMID and/or the DSMB by teleconference as requested.

9.6.2. Data and Safety Monitoring Board (DSMB)

Safety oversight will be conducted by a DSMB that is an independent group of experts that monitors subject safety and advises DMID. The DSMB members will be separate and independent of study personnel participating in this trial and should not have scientific, financial, or other conflicts of interest related to this trial. The DSMB will consist of members with appropriate expertise to contribute to the interpretation of the data from this trial.

The DSMB will operate under the rules of a DMID-approved charter that will be written at the organizational meeting of the DSMB. Procedures for DSMB reviews/meetings will be defined in the charter. Reports may include enrollment and demographic information, medical history, concomitant medications, physical assessments, clinical laboratory values, dosing compliance,

and solicited and unsolicited AE/SAEs. The DSMB will review SAEs on a regular basis and ad hoc during this trial. The DMID Medical Monitor and the ISM (as deemed necessary per [Section 9.6.1](#)) will be responsible for reviewing SAEs in real time.

Additional data may be requested by the DSMB, and interim statistical reports may be generated as deemed necessary and appropriate by DMID. The DSMB may receive data in aggregate and presented by treatment arm (pregnant women, infants). The DSMB may also be provided with expected and observed rates of the solicited AEs in an unblinded fashion and may request the treatment assignment be unblinded for an individual subject if required for safety assessment.

The DSMB will review grouped and unblinded data in the closed session only. As an outcome of each review/meeting, the DSMB will make a recommendation as to the advisability of proceeding with study vaccinations (as applicable), and to continue, modify, or terminate this trial.

The DSMB will conduct the following reviews:

- When safety data collected through Day 8 is available for 25% of pregnant study subjects.
- Ad hoc when a halting rule is met or DMID/DSMB chair may convene an ad hoc meeting if there are immediate concerns regarding observations during this trial.
- Final review meeting: 6 to 8 months after clinical database lock to review the cumulative unblinded data for this trial. The data will be provided in a standard summary format. The DSMB may be asked to provide recommendations in response to questions posed by DMID.

